EDC	Electronic data capture
EU	European Commission
FSH	Follicle-stimulating hormone
GLP	Good Laboratory Practice
HBsAg	Hepatitis B surface antigen
HCV	Hepatitis C
HIV	Human immunodeficiency virus
HR	Heart rate
IB	Investigator's Brochure
ICH	International Conference on Harmonisation
ICRP	International Committee for Radiological Protection
IEC	Independent Ethics Committee
IMP	Investigational medicinal product
IND	Investigational new drug (application)
INR	International normalized ratio
IRB	Institutional review board
IV	Intravenous
LPLO	Last participant, last observation
MAD	Multiple-ascending doses
MRI	Magnetic resonance imaging
MTD	Maximum tolerated dose

NOAC Non-vitamin K antagonist oral anticoagulant

NOAEL No-observed-adverse-effect level

NSAESI Non-serious adverse event of special interest

OTC Over-the-counter

PAM Positive allosteric modulator

PD Pharmacodynamic
PK Pharmacokinetic
QRS QRS complex
QT QT interval

QTc QT corrected for heart rate

QTca Individual probabilistic corrected QT

QTcF QT corrected for heart rate using the Fridericia's

correction factor

RBC Red blood cell

RO Receptor occupancy
ROI Region of interest

RR RR interval

SAD Single-ascending dose
SAE Serious adverse event
SoA Schedule of activities

SOP Standard operating procedure

SUSAR Suspected unexpected serious adverse reactions

TQT Thorough QT

ULN Upper limit of normal

V Volume

V/F Apparent volume of distribution

VPA Valproic acid
WBC White blood cell

1. PROTOCOL SUMMARY

1.1 SYNOPSIS

PROTOCOL TITLE: A NON-RANDOMIZED, OPEN LABEL, ADAPTIVE, PARALLEL

GROUP, HUMAN POSITRON EMISSION TOMOGRAPHY (PET)
STUDY TO ASSESS OCCUPANCY OF BRAIN α5-CONTAINING
GABA
A RECEPTORS OF RO7017773 USING [11C] RO15-4513

FOLLOWING SINGLE ORAL DOSES IN HEALTHY

PARTICIPANTS

SHORT TITLE OPEN LABEL, ADAPTIVE, PARALLEL GROUP PET STUDY

USING RO7017773 AND [11C] RO15-4513

PROTOCOL NUMBER: BP40257

VERSION: 2

TEST PRODUCT: RO7017773

PHASE:

RATIONALE

This study aims to quantify the level of receptor occupancy of RO7017773 using PET tracer [11C]Ro15-4513 after varying single oral doses of RO7017773. The measurement of brain receptor occupancy (RO) obtained using positron emission tomography (PET) is critically important to characterize pharmacokinetic (PK)-RO relationship and will

This will be the first study assessing GABA_A $\alpha 5$ receptor occupancy following single doses of RO7017773 in healthy participants using PET and the [11 C]Ro15-4513 PET tracer. The study will estimate the doses of RO7017773 which displaces the binding of the radiolabeled GABA_A $\alpha 5$ ligand [11 C]Ro15-4513 to the receptors in the brain.

OBJECTIVES AND ENDPOINTS

	Objectives		Endpoints
Primary			
RO7017773 brain occupa subtypes (co single oral do	e relationship between plasma concentration and incy of GABA _A receptor ntaining the α5 subunit) after oses of RO7017773 using 513 PET tracer.	•	Occupancy of brain α 5-containing GABA _A receptors by RO7017773 in selected regions of interest (ROIs). RO7017773 plasma concentrations.
Secondary			
	e safety and tolerability of oses of RO7017773.	•	Incidence and severity of AE. Changes in vital signs, physical findings, ECG parameters, and clinical laboratory results during and following RO7017773 administration.
Tertiary/Explora	tory		
•		•	

OVERALL DESIGN

Study Design

This is a single dose (SD), non-randomized, open-label, adaptive, parallel group study with the purpose of investigating the occupancy of α 5-containing GABA_A receptors by RO7017773 in healthy participants.

Healthy participants will be admitted to the clinical research unit on Day –1 of each imaging session. On Day 1 of the first imaging session, participant will have a baseline PET scan and will be discharged after its completion. At the second imaging session, participant will receive a single dose of RO7017773,

The timings of PET scans and PK sampling may change based on review of emerging data or study logistical requirements. Participants will be discharged at least 48 hours after RO7017773 administration (at the discretion of the Investigator) when all assessments have been completed.

For each participant, the imaging session 2 (on-treatment PET scans 1 and 2) will be at least 7 days after imaging session 1 (baseline scan).

At the start of each PET scan, participants will receive an intravenous dose of the radiolabeled tracer [¹¹C]Ro15-4513. During imaging session 2, a single oral dose of RO7017773 will be administered before the first on-treatment PET scan. Up to dose levels, between are anticipated to be tested allowing the extent and duration of brain GABA_A-α5 receptor occupancy of varying single oral doses of RO7017773 in healthy participants to be measured using the [¹¹C]Ro15-4513 PET tracer.

-Participants will receive no more than 2 doses of RO/01/7/3 (e.g., in case an on-treatment PET/CT scan needs to be re-scheduled for technical or logistical reasons), and 3 doses of the radiolabeled ligand, [11C]Ro15-4513, throughout the study. Participants will attend the clinical research unit for a safety follow-up visit 5 to 10 days after the last dose of RO7017773.

This study will have an adaptive design to adequately evaluate the exposure versus RO relationship. The doses to be tested in the subsequent cohorts of participants will be selected after review by the Investigator, PET specialist and Sponsor of the available RO, PK, PK-RO, safety and tolerability data at the previous dose levels. The doses will be selected *in order to obtain a wide enough range of receptor occupancies to allow adequate model parameter estimation of the RO7017773 exposure-RO relationship* based on RO7017773 concentrations that will span as much of the occupancy range as possible. If a dose level causes any safety concerns, the same or a higher dose level will not be tested in any other participants. Following review of available data from the previous dose level(s), timing of on-treatment PET scans and PK sampling may also change.

Treatment Groups and Duration

- Screening: Up to 4 weeks
- Imaging Session 1 (baseline PET scan): Day –1 to Day 1
- Imaging Session 2 (on-treatment PET scan): Day -1¹⁾ to
- · Safety follow-up: 5 to 10 Days after last dose

All participants will receive a single dose of the IMP RO7017773. The PET tracer [\$^{11}C]Ro15-4513 is non-IMP.

Length of Study

The total duration of the study for each participant will be up to 8 weeks.

End of Study

A participant is considered to have completed the study if he/she has completed the safety follow-up visit. The end of the study is defined as the date when the last participant last observation (LPLO) occurs. LPLO is expected to occur approximately 5 to 10 days after the last participant last dose of RO7017773.

PARTICIPANT POPULATION

The participants of this study are healthy volunteers between 23 and 55 years of age, inclusive, who fulfill all the inclusion criteria.

Inclusion Criteria

Informed Consent

 Able and willing to provide written informed consent and to comply with the study protocol according to ICH and local regulations.

Age

Healthy participants aged 23 to 55 years of age, inclusive, at the time of signing the informed consent.

Type of Participants and Disease Characteristics

Healthy, as judged by the Investigator.

Healthy status is defined by absence of evidence of any active or chronic disease following a detailed medical and surgical history, a complete physical examination including vital signs, 12-lead ECG, hematology, blood chemistry, serology and urinalysis.

[figure not shown]
¹⁾Admission for imaging session 2 will be at least 6 days after the baseline PET scan.

Weight

4. Body Mass Index (BMI) of 18 to 30 kg/m², inclusive at screening.

Sex

- Male and female participants
- a) Female Participants

b) Male Participants

During the treatment period and for at least 90 days after the last dose of study drug, agreement to:

- Remain abstinent (refrain from heterosexual intercourse) or use contraceptive
 measures such as a condom, with partners who are WOCBP, or pregnant female
 partners, to avoid exposing the embryo to study treatment.
- Refrain from donating sperm 90 days after the last dose.

The contraception and abstinence requirements are intended to prevent exposure of an embryo to the study treatment. The reliability of sexual abstinence for male and/or female enrollment eligibility needs to be evaluated in relation to the duration of the clinical study and the preferred and usual lifestyle of the participant. Periodic abstinence (e.g., calendar, ovulation, symptothermal, or post-ovulation methods) and withdrawal are not acceptable methods of contraception.

Exclusion Criteria

Participants are excluded from the study if any of the following criteria apply:

Medical Conditions

- Any condition or disease detected during the medical interview/physical examination that
 would render the participant unsuitable for the study, place the participant at undue risk or
 interfere with the ability of the participant to complete the study, as determined by the
 Investigator.
- History or evidence of any medical condition potentially altering the absorption, metabolism
 or elimination of drugs. This includes a surgical history of the gastrointestinal tract affecting
 gastric motility or altering the gastrointestinal tract.
- 3. History of any clinically significant gastrointestinal, renal, hepatic, bronchopulmonary, neurological, psychiatric, cardiovascular, endocrinological, hematological or allergic disease, metabolic disorder, hypofertility, cancer or cirrhosis.
- History of convulsions (other than benign febrile convulsions of childhood) including epilepsy, or personal history of significant cerebral trauma or CNS infections (e.g., meningitis).
- Clinically significant abnormal finding from the MRI performed after the initial screening examination.
- 6. A history of clinically significant hypersensitivity (e.g., drugs, excipients) or allergic reactions.
- 7. Any major illness within one month before the screening examination or any febrile illness within one week prior to screening and up to first study drug administration.
- 8. Abnormal blood pressure, i.e., systolic blood pressure (SBP) greater than 140 or less than 90 mm Hg, and diastolic blood pressure (DBP) greater than 90 or less than 50 mm Hg.

- Abnormal pulse rate, resting pulse rate greater than 100 or less than 40 bpm.
- History or presence of clinically significant ECG abnormalities before study drug administration (e.g., PQ/PR interval > 210 ms, QTcF > 450 ms (> 470 ms females) or cardiovascular disease (e.g., cardiac insufficiency, coronary artery disease, cardiomyopathy, congestive heart failure, family history of congenital long QT syndrome, family history of sudden death).
- 11. Clinically significant abnormalities in laboratory test results (including hepatic and renal panels, complete blood count, chemistry panel and urinalysis). In the case of uncertain or questionable results, tests performed during screening may be repeated before randomization to confirm eligibility.
- 12. Participants who, in the Investigator's judgment, pose a suicidal or homicidal risk, or any participant with a history of suicidal or homicidal attempts.

Prior/Concomitant Therapy

 Participants likely to need concomitant medication during the study period (including for dental conditions).

Prior/Concurrent Clinical Study Experience

- 14. Participation in an investigational drug or device study within 90 days prior to screening, as calculated from the day of follow-up from the previous study, or more than 4 times a year.
- 15. Previous inclusion in a research and/or medical protocol involving PET or radiological investigations (within the last 12 months).

Diagnostic Assessments

- Positive test for drugs of abuse or alcohol.
- 17. For WONCBP, a positive pregnancy test.
- Show evidence of human immunodeficiency virus (HIV) infection and/or positive human HIV antibodies.
- Positive result on hepatitis B (HBV) or hepatitis C (HCV), presence of hepatitis B surface antigen (HBsAg) or positive hepatitis C antibody test result at screening or within 3 months prior to starting study treatment.

Other Exclusions

- Dietary restrictions that would prohibit the consumption of standardized meals.
- Any suspicion or history of alcohol abuse and/or suspicion of regular consumption of drug of abuse or previous history of or treatment for a dependence disorder.
- 22. Participants who regularly smoke more than 5 cigarettes daily or equivalent and unable or unwilling not to smoke during the in-house period.
- 23. Participants who have donated over 500 mL of blood or blood products or had significant blood loss within 3 months prior to screening.
- 24. Participants under judicial supervision, guardianship or curatorship.
- 25. Presence of a cardiac pacemaker or other electronic device; ferromagnetic metal foreign bodies in vulnerable positions; presence of certain tattoos that might make it unsafe for an MRI; participant working as a machinist, welder or metal worker; claustrophobia; as assessed by a standard pre MRI questionnaire.
- 26. Occupational radiation exposure or radiation exposure Exposure to ionising radiation in from medical diagnostic or treatments research over the past 12 months, that would result in a dose in excess of 10 mSv which when combined with the planned exposure from this study would result in an effective dose in excess of 10 mSv.
- Contraindication for arterial cannulation; Allen's test indicating potential risk in placement of the arterial cannula.

NUMBER OF PARTICIPANTS

It is anticipated that a maximum of 15 participants will be enrolled in the study. At each anticipated dose level, up to 2 to 3 participants may be enrolled with 2 participants per cohort.

CONCOMITANT MEDICATIONS

Permitted Therapies

•

 Acetaminophen/paracetamol is allowed up to a maximum dose of 2 g/day up to 48 hours prior to dosing and after the in-house period, but should not exceed 4 g total during the week prior to dosing.

Prohibited Therapies

Use of the following therapies is prohibited during the study and for at least 30 days or at least 5 half-lives of the medication prior to initiation of study treatment (whichever is longer), unless otherwise specified below:

 Any prescribed or over-the-counter medication (including herbal products, vitamin, mineral, energy drinks and dietary supplements).

 Acetylsalicylic acid and other anti-platelet and anti-coagulation medication, e.g., adenosine diphosphate (ADP) receptor inhibitors, heparin, warfarin and non-vitamin K antagonist oral anticoagulants (NOACs).

1.3 SCHEDULE OF ACTIVITIES

The schedule of the activities is provided in Table 1 and Table 2.

Table 1 Schedule of Activities - Main Table

Visit	Screening	Imaging Session 1 (baseline)		Imag	Imaging Session 2 (on-treatment) ^a						Imaging Session 2 (on-treatment) ^a					
Day(s) (relative to PET scans)	Up to -28	-1	1	-1	1	2	3	5-10 days								
nformed Consent	X															
Medical History	х															
Physical Examination	X							X								
Height & weight ^c	X	X		X				X								
Admission		X		X												
n-house Period		X	х	х	х	X	Х									
Discharge			х				Х									
/ital Signs ^d	Х	Х	χ ^e	Х	5	Х	Х	х								
ECG-12 lead ^f	х	X	χ ^e	4 ^g	4	X	х	X								
Serology	Х															
Pregnancy Test h	Х	Х		Х				х								
Hormone Panel	X															
Alcohol Breath Test	х	X		х												
Urine Drugs of abuse	х	х		х												
Jrinalysis	х	х		х				х								
Blood Chemistry	х	X		х				х								
Hematology	х	х		х				х								
Coagulation	х															
Standardised meal		X	х	х	х	х	х									
MRI Scan ^j	х															
Allen's test	Х	Х	Х	Х	Х											
Administration of RO7017773					х											
niection [¹¹ C]Ro015-4513			Х		2											
Arterial blood sampling for																
¹¹ C]Ro015-4513 radioactivity measurement			x		x											
Previous and Concomitant	х	х	х	х	х	х	х	х								
	х	х	х	х	х	х	х	х								

- a) For each participant, imaging session 2 (on-treatment PET/CT scans) will occur approximately 7 days after imaging session 1 (baseline scan).
- b) Safety and follow-up visit to be done 5 to 10 days after the RO7017773 administration.
- c) Height at screening only, when body mass index (BMI) will be derived.
- d) Vital signs will include blood pressure, pulse rate and body temperature. Temperature will be recorded on Day 1 of imaging session 2 only. All measurements will be taken after the participant has rested in a supine position for at least 5 minutes.

Table 1 Schedule of Activities – Main Table (cont.)

- e) Prior to the PET scan and before discharge from the unit.
- f) Triplicate 12-lead ECGs will be collected after the participant has rested in a supine position for at least 10 minutes.
- g) ECGs will be time-matched on Day 1 and Day -1 of imaging session 2 (see Detailed table).
- h) Pregnancy test for females of childbearing potential only. Serum test at screening, urine test at Day –1 of imaging session 1 and 2 and follow-up. The screening pregnancy test can be used for the MRI scan if done on the day of the MRI scan otherwise an additional urine test on day of MRI scan will be performed.
- i) Hormonal panel is for post-menopausal women only.
- j) Participants will complete an MRI questionnaire before the scan, to exclude unsuitable and unwilling participants. The structural MRI scan may be done at a separate visit, provided the results are available before the baseline PET scan. The MRI scan should be performed within 60 days of screening.
- I) RO7017773 will be administered orally with water, in the morning of Day 1 of imaging session 2 after an overnight fast of at least 10 hours. Water will be allowed ad libitum until 1 hour prior to dosing and from 1 hour post-dosing. Occasionally, a technical failure (such as unsuccessful tracer synthesis) or study logistical requirements may require one or both on-treatment PET scans to be rescheduled.

Table 2 Schedule of Activities – Imaging Session 2, Detailed Table

		Imaging Session 2 (on-treatment)												
			Day 1											
Times relative to RO administration	Predose equivalent	2h	6h	11h	Predose	0h	2h	3.5h	4.5h	5h	6h	9h	10.5h	11h
Administration of RO7017773						х								
Injection [¹¹ C]Ro015-4513								x				X		
Vital Signs (blood pressure and pulse rate)					х		х		х		х			х
Temperature					x		х				х			
ECG-12 lead	х	Х	х	х	x		х				х			х

2. INTRODUCTION

2.1 STUDY RATIONALE

[figure not shown]
This study aims to quantify the level of receptor occupancy of RO7017773 using PET tracer [11C]Ro15-4513 after varying single oral doses of RO7017773. The measurement of brain receptor occupancy (RO) obtained using positron emission tomography (PET) is critically important to characterize PK-RO relationship and

[figure not shown]
. Each participant will undergo a baseline PET/CT scan and two on-treatment PET/CT scans, allowing the extent and duration of brain GABA_A- α 5 receptor occupancy of varying single oral doses of RO7017773 in healthy volunteers to be measured using the [11 C]Ro15-4513 PET tracer. The study will estimate the doses of RO7017773 which displaces the binding of the radiolabeled GABA_A α 5 ligand [11 C]Ro15-4513 to the receptors in the brain.

The rationale for the study design is provided in Section 4.2.

2.2 BACKGROUND

A detailed description of the chemistry, pharmacology, efficacy and safety of RO7017773 is provided in the Investigator's Brochure (RO7017773 Investigator's Brochure).

2.2.2 Background on PET Tracer [11C]Ro15-4513

In this study, the PET ligand [11 C]Ro15-4513 (non-Investigational Medicinal Product [NIMP]) will be given to participants at the start of each PET/CT scan, to quantify the level of receptor occupancy at α 5-containing GABA_A receptors after single oral doses of RO7017773.

[\$^{11}C]Ro15-4513\$ is a partially selective ligand for the GABA\$_{A}\$ \$\alpha 5\$ receptor subtype with relatively higher in vitro affinity for the \$\alpha 5\$ subunit-containing GABA\$_{A}\$ receptor than for other \$\alpha\$ subunits. Ro15-4513 has 10-20-fold higher in vitro affinity for \$\alpha 5\$ subunit-containing GABA\$_{A}\$ receptors (Ki=0.7 nmol/I) compared with \$\alpha 1\$, \$\alpha 2\$, and \$\alpha 3\$ subunit-containing receptors (Ki=7–10 nmol/I).

[figure not shown]
In previous PET studies, binding of [11 C]Ro15-4513 was predominantly seen in the hippocampus, amygdala, anterior cingulate cortex, and insular cortex, consistent with the evidence that it is selectively labelling GABA_A receptors containing the α 5 subunit (Myers et al 2017). No adverse effects of the PET tracer have been reported to date.

The potential risks for any healthy participants due to the treatment of RO7017773 or study-related procedures are considered minimal and are outweighed by the potential to develop a new treatment for ASD. Further information about the known and expected benefits in the context of potential risks and reasonably expected adverse events of RO7017773 is provided in the Investigator's Brochure (RO7017773 Investigator's Brochure).

3. OBJECTIVES AND ENDPOINTS

The objectives and corresponding endpoints are provided in Table 4.

Table 4 Objectives and Endpoints

	Objectives	Endpoints				
Pri	mary					
•	To assess the relationship between RO7017773 plasma concentration and brain occupancy of GABA _A receptor subtypes (containing the $\alpha 5$ subunit) after single oral doses of RO7017773 using [11 C]Ro15-4513 PET tracer.	•	Occupancy of brain α 5-containing GABA _A receptors by RO7017773 in selected regions of interest (ROIs). RO7017773 plasma concentrations.			
Sec	condary					
•	To assess the safety and tolerability of	•	Incidence and severity of AE.			
	single oral doses of RO7017773.	•	Changes in vital signs, physical findings, ECG parameters, and clinical laboratory results during and following RO7017773 administration.			

		Objectives	Endpoints					
Terti	iary/Explora	atory						
•			•		Ĩ			

4. STUDY DESIGN

4.1 OVERALL DESIGN

This is a single dose (SD).

non-randomized, open-label, adaptive, parallel group study with the purpose of investigating the occupancy of α5-containing GABA_A receptors by RO7017773 in healthy participants.

Healthy participants will be admitted to the clinical research unit on Day -1 of each imaging session. On Day 1 of the first imaging session, participant will have a baseline PET/CT scan and will be discharged after its completion.

The timings of PET scans

and PK sampling may change based on review of emerging data or study logistical requirements. Participants will be discharged at least 48 hours after RO7017773 administration (at the discretion of the Investigator) when all assessments have been completed. Participants stay in the clinical unit may be extended based on review of

For each participant, the imaging session 2 (on-treatment PET/CT scans 1 and 2) will be at least 7 days after imaging session 1 (baseline scan).

At the start of each PET/CT scan, participants will receive an intravenous dose of the radiolabeled tracer [11C]Ro15-4513. Thus, during the study, each participant will receive three doses of the radiolabeled tracer: one IV dose at imaging session 1 (at the beginning of the baseline PET/CT scan) and two IV doses at imaging session 2 (at the beginning of each on-treatment PET/CT scan; see Section 6.1).

During imaging session 2, a single oral dose of RO7017773 will be administered before the first on-treatment PET/CT scan (see Section 6.1).

At each anticipated dose level, up to 2 to 3 participants are expected to be enrolled (see Section 9.2).

If one, or both, on-treatment PET/CT scans need to be rescheduled, (e.g., due to a technical failure or logistical reasons), participants may receive a second dose of RO7017773 (at least 72 h after their initial dose). In such cases, the entire imaging session may be repeated at a later date. The subject may be discharged and readmitted to the research unit between doses. Admission (Day -1) procedures will be repeated on each admission. Participants

will receive no more than 2 doses of RO7017773, and 3 doses of the radiolabeled ligand, [11C]Ro15-4513, throughout the study. Participants will attend the clinical research unit for a safety follow-up visit 5 to 10 days after the last dose of RO7017773.

This study will have an adaptive design to adequately evaluate the exposure versus RO relationship.

The doses will be selected in order to obtain a wide enough range of receptor occupancies to allow adequate model parameter estimation of the RO7017773 exposure-RO relationship based on RO7017773 concentrations that will span

4.1.1 Length of the Study

as much of the occupancy range as possible.

The total duration of the study for each participant will be up to 8 weeks divided as follows:

- Screening: Up to 4 weeks
- Imaging Session 1 (baseline PET/CT scan): Day –1 to Day 1
- Imaging Session 2 (on-treatment PET/CT scan): Day -1¹⁾ to
- Safety follow-up: 5 to 10 Days after last dose.

¹⁾Admission for imaging session 2 will be at least 6 days after the baseline PET/CT scan *if arterial sampling required.*

4.1.2 Selection of Dose Levels for Subsequent Cohorts and Timing of PET/CT scans and PK sampling S

The choice of the next dose level(s) will be made following review, by the Investigator, the PET specialist and Sponsor, of RO data at the previous dose level(s), and all available PK, PK-RO data, safety and tolerability data as outlined in Appendix 6 and in Section 4.3.

If a dose level causes any safety concerns, the same or a higher dose level will not be tested in any other participants (see Section 2.3).

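### Does the permission in Section 4.1 to repeat a whole imaging session break its own cap of three tracer doses?

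*Combined protocol and SAP*

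**What the plan says.** Section 4.1 (Overall Design) sets the planned tracer use: "each participant will receive three doses of the radiolabeled tracer: one IV dose at imaging session 1", and "two IV doses at imaging session 2 (at the beginning of each on-treatment PET/CT scan". It then deals with sessions that go wrong. The trigger is broad: "If one, or both, on-treatment PET/CT scans need to be rescheduled". Two permissions follow. The first concerns study drug: "participants may receive a second dose of RO7017773 (at least 72 h after their initial dose". The second concerns the session: "In such cases, the entire imaging session may be repeated at a later date". Two sentences on discharge, readmission and repeating the Day -1 procedures come next, and then the limit: participants "will receive no more than 2 doses of RO7017773, and 3 doses of the radiolabeled ligand", counted over the whole study.

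The synopsis (Section 1.1) gives the same two limits in one sentence. It names a rescheduled on-treatment scan as its example of why a second dose of study drug might be needed, and it still holds tracer at three. Its readable text has no sentence about repeating a whole session.

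A footnote to Table 1 (Section 1.3) explains how rescheduling arises: "Occasionally, a technical failure (such as unsuccessful tracer synthesis) or study logistical requirements may require one or both on-treatment PET scans to be rescheduled".

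**The concern.** Planned tracer use equals the cap, so any injection beyond the plan is over the limit. The repeat sentence refers back to a trigger that expressly includes the loss of a single scan, and by then the other scan may already have used its tracer.

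The documents show how this can happen. Table 2, in its row "Times relative to RO administration", places the two injections in the 3.5 h and 9 h columns, 9 - 3.5 = 5.5 h apart. Table 6 has each tracer solution made up just before it is injected. Scan 1 can therefore be finished before the synthesis for scan 2 fails, and repeating both scans would need a fourth injection.

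Two things would be at stake. One is an extra radioactive injection in a healthy volunteer. The other is a second dose of study drug given when too little tracer remains for the session it was meant to support.

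**Working it through.** **Inputs.** One injection per scan, one scan at baseline, two scans in imaging session 2 and a cap of 3 (all Section 4.1). The maximum activity is 370 MBq per scan (Table 6).

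**The plan's own figure.** 1 + 2 = 3, which matches the stated number and equals the cap. No stated figure is wrong.

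**What a repeat does.** Let k be the number of on-treatment injections already given when the session breaks down.

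- Tracer left under the cap: 3 - (1 + k) = 2 - k
- Total after a full two-scan repeat: 1 + k + 2
- Scans still without an injection: 2 - k
- Total if only those scans are done: 1 + k + (2 - k) = 3

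| k | Left under cap | Full-repeat total | Scans not yet injected | Total if only those are done |
|---|---|---|---|---|
| 0 | 2 | 3 | 2 | 3 |
| 1 | 1 | 4 | 1 | 3 |
| 2 | 0 | 5 | 0 | 3 |

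A full repeat fits the cap when k = 0. It exceeds the cap by 1 when k = 1 and by 2 when k = 2. In activity, the planned maximum is 3 × 370 = 1110 MBq, and a fourth injection would make it 4 × 370 = 1480 MBq.

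**Can the two sentences be obeyed together?** The repeat sentence says what may be done; the cap says what will not be exceeded. No sentence requires a fourth injection, and one forbids it. The tracer left under the cap always equals the number of scans not yet injected (both are 2 - k), so the cap never blocks a scan that lost its slot before injection. The one technical failure the protocol names, a failed synthesis, is of that kind and uses no injection.

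**Where the cap does bite.** If a scan fails after injection, its tracer is spent. With k = 1 and scan 1 unusable, one injection is left for two scans. With k = 2, none is left. The result is a lost observation, not a breach of the limit.

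**Effect on the analysis.** Section 9.1 tests no hypothesis, and Section 9.4.4 lists occupancy without formal analysis. Section 4.2.2 ties plasma samples to each on-treatment scan, so a scan done after a second dose brings its own concentrations to the exposure-occupancy model. The PK/PD population in Table 7 needs at least one on-treatment scan, subject to its exclusions for deviations and incomplete data.

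**The case for a change.** The best case for a defect is that the repeat sentence expressly reaches the one-scan case and no readable text confines it to sessions with no injection. If the cap governs, a participant with scan 1 done has one injection left, so the entire session the sentence offers cannot be carried out as two scans. The permission for a second dose of study drug is not linked to remaining tracer either. Exclusion criterion 26 adds prior exposure to the exposure planned in this study, and the plan is three scans. Staff would read this clause on the day a synthesis fails, when a plain instruction helps most.

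Part of this stands. Section 4.1 does not say what a repeat contains once one on-treatment injection has been used, nor whether a second dose of study drug depends on remaining tracer. Session may mean both scans, or the admission and dosing sequence that the next two sentences describe; the text does not settle which.

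The fourth injection does not stand. It arises only if the repeat sentence is read without the cap that closes its own paragraph and that the synopsis restates alongside rescheduling. The missing link between study drug and tracer is an absent rule, not a conflict between two rules.

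**Conclusion.** No change follows. This is a gap in wording that the site and sponsor can fill sensibly within limits already set, and it is not an error of arithmetic. With the cap observed, the excess over three injections is 0 in every case. The excess of 1 (4 against 3) needs both an on-treatment injection already given and a reading that sets the cap aside. Where a scan is lost before injection, the cap leaves enough tracer for every scan not yet injected. Where a scan fails after injection, the cost is that observation. No stated number, analysis or exposure limit depends on how the gap is filled.

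This rests on three assumptions. The cap binds over the whole study, as its words say. No text missing from the public copy says otherwise: the study-drug dosing instructions in Table 6, some Table 1 footnote text and the content of Section 9.4.5 cannot be read. Failed scans are uncommon: the Table 1 footnote calls them occasional, but the documents give no rate. No view is taken here on what a repeated session should contain.
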